	• To assess the immunogenicity of a single dose of QVLP (30 µg/strain) with AS03 adjuvant compared to QVLP (30 µg/strain) (unadjuvanted) and Fluzone HD Quad, as measured by hemagglutination inhibition (HI) assay against homologous influenza strains.
Secondary Objectives:	The secondary objectives of this study are: Immunogenicity: • To assess the immunogenicity of a single dose of QVLP (30 μg/strain) with AS03 adjuvant compared to QVLP (30 μg/strain) (unadjuvanted) and Fluzone HD Quad, as measured by microneutralization (MN) assay against homologous influenza strains; • To assess the immunogenicity of a single dose of QVLP (30 μg/strain) with AS03 adjuvant compared to QVLP (30 μg/strain) (unadjuvanted) and Fluzone HD Quad, as measured by HI assay against heterologous influenza strains; • To assess the immunogenicity of a single dose of QVLP (30 μg/strain) with AS03 adjuvant compared to QVLP (30 μg/strain) (unadjuvanted) and Fluzone HD Quad, as measured by HI (homologous and heterologous influenza strains) and MN (homologous influenza strains) assays, stratified by prior influenza vaccination status, if >25% of the enrolled subjects have received a standard influenza vaccine during the 12 months prior to study vaccination; • To evaluate the persistence of antibody responses, as determined by HI titers against homologous influenza strains, at 6 and 12 months post-vaccination;
	_

	(30 μg/strain) (unadjuvanted) and Fluzone HD Quad, stratified by prior influenza vaccination status, if >25% of the enrolled subjects have received a standard influenza vaccine during the 12 months prior to study vaccination.	
Number of Planned Subjects:	Approximately 120 healthy adult subjects 65 years of age and older are planned for randomization in a 1:1:1 ratio to receive QVLP at a dose of 30 µg/strain with AS03 adjuvant or QVLP (30 µg/strain) (unadjuvanted) or Fluzone HD Quad.	
Sample Size Determination:	The sample size up to approximately 120 subjects with 40 subjects in each treatment group will make it possible to perform the initial evaluation of vaccine immunogenicity and detect gross differences in rates of adverse events. The sample size is not large enough to detect all types of adverse reactions, including less frequent or rare events. The objective of this study is to quantify the type, percentage, duration, intensity, and relationship of common post-vaccination safety events to determine if they differ clinically among the treatment groups.	

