1.3.1 Safety Overview for QVLP

This section summarizes the safety data obtained from the eight completed clinical trials performed with unadjuvanted QVLP (CP-Q12VLP-004, CP-Q13VLP-007, CP-Q13VLP-008, CP-Q14VLP-009, CP-Q14VLP-010, CP-PRO-QVLP-011, CP-PRO-QVLP-012, and CP-PRO-QVLP-014) and adjuvanted QVLP (CP-Q13VLP-008); see Table 2 for a description of the basic design of these studies, status, and exposure. The incidence of local and systemic reactions observed within seven days post-vaccination in these eight studies was consistent with the known safety profile for commercial influenza vaccines. The most frequently reported (≥ 1.0 % of subjects) unsolicited TEAEs within 21 days of vaccine administration included arthralgia, back pain, diarrhea, fatigue, headache, musculoskeletal pain, myalgia, nasal congestion, nasopharyngitis, nausea, oropharyngeal pain, pain in extremity, rhinorrhea, and upper respiratory

infection. No notable differences in the incidence of these events were observed between the QVLP groups and the active comparators or placebo groups. No safety issues and no notable trends were observed with respect to vital signs, clinical laboratory, or physical examinations in any of the eight completed studies.

In these eight completed clinical trials, the incidence of subjects with at least one SAE during the overall study period was < 5.0 % in the QVLP groups. No apparent trends with respect to the number or types of SAEs were noted. However, there were more SAEs reported among the elderly subjects 65 years of age and older compared to the adult subjects 18 to 64 years old. Only three SAEs were considered by the site Investigator to be related to the study treatment (all in the elderly subjects 65 years of age and older group) and only one of these was for the QVLP group: a possible anaphylactic reaction in one subject in the 30 μ g/strain QVLP group. There were fifteen subjects in the QVLP group who had treatment-emergent adverse events (TEAEs) leading to withdrawal from the study and all these subjects received the 30 μ g/strain dose and were 65 years and older. Only one NOCD for adult subjects 18 to 64 years old who received QVLP and only six NOCDs for elderly subjects 65 years and older who received QVLP were reported that were considered by the site investigators to be vaccine-related.

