12.5.1 Analysis of Primary Endpoints

The primary safety endpoints are defined in Section 10.2.2.1.

The original terms used in the eCRFs by Investigators to identify AEs will be coded using the Medical Dictionary for Regulatory Activities (MedDRA®). All eCRF reported AEs with onset post-vaccination will be included in the safety analyses.

Safety and tolerability endpoints (immediate AEs [30 minutes post-vaccination], solicited local and systemic AEs, unsolicited AEs, SAEs, AEs leading to subject withdrawal, AESIs, MAAEs, NOCDs, and deaths) will be summarized by treatment using descriptive statistics.

Laboratory (biochemical, haematological, and urine) data will be summarized by type of laboratory test. Reference ranges and markedly abnormal results will be used in the summary of laboratory data. Descriptive statistics will be calculated for each laboratory test at Baseline and at each scheduled timepoint (Day 3 and Day 28). Changes from Baseline results will be presented in pre- versus post-treatment cross tabulations (with classes for below, within, and above normal ranges).

Special attention will be given to those subjects who die, who discontinue from the study due to an AE, who experience an SAE (e.g. summaries, listings, and narrative preparation may be provided, as appropriate), or who experience an AESI (see Section 13.1.3).

Analyses of primary safety endpoints will include each group as a whole. For the following categories, AE information will also be presented by gender (male and female) and race (Caucasian or White; Black or African American; Asian) for the overall population (65 years of age and older):

- Immediate solicited and unsolicited AEs up to 30 minutes after vaccination;
- Solicited local and systemic AEs within Days 0 to 7;
- Most frequent unsolicited AEs within 28 days after vaccination;
- AESIs;
- MAAEs;
- SAEs;
- AEs leading to death;
- AEs leading to withdrawal.

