# 3. Investigational Plan

# 3.1. Overall Study Design and Plan

This randomized, partially-blinded, active comparator-controlled multi-center, Phase 1/2 study will be conducted at multiple sites to evaluate the safety, tolerability, and immunogenicity of an adjuvanted seasonal recombinant quadrivalent VLP influenza vaccine in adults 65 years of age and older. Overall approximately 120 healthy male and female subjects 65 years of age and older will be enrolled evenly into one of three parallel treatment groups and subjects will be stratified by age into two groups (65 to 74 years of age and 75 years of age and older) and by prior influenza vaccination status (defined as having received a standard influenza vaccine during the 12 months prior to study vaccination). Before protocol version 4.0 became effective:

- In protocol version 2.0, a different randomization was in place with 2 additional treatment groups (QVLP adjuvanted with AS03 (half dose) 15 μg/strain and QVLP adjuvanted with AS03 (half dose) 45 μg/strain) and without prior influenza vaccine status as randomization stratification factor. The enrollment of these two treatment groups was stopped per protocol version 3.0. The number of subjects randomized into these two treatment groups will be documented in the CSR. The six treatment groups included three dose levels of QVLP (15 μg/strain, 30 μg/strain, and 45 μg/strain) with the full dose or QVLP (30 μg/strain) with the half dose of adjuvant AS03, unadjuvanted full dose of QVLP (30 μg/strain), and the active comparator Fluzone HD Quad.
- In protocol version 3.0, there was 3 additional treatments groups (QVLP adjuvanted with AS03 15 μg/strain, QVLP adjuvanted with AS03 (half dose) 30 μg/strain and QVLP adjuvanted with AS03 45 μg/strain). The enrollment of these 3 treatment groups was stopped per protocol version 4.0. The number of subjects randomized into these three treatment groups will be documented in the CSR. Moreover, the planned number of subjects has been decreased 50 to 40 by treatment group.

The three remaining treatment groups include QVLP adjuvanted with AS03 (30 µg/strain), unadjuvanted QVLP (30 µg/strain), and the active comparator Fluzone HD Quad.

**Table 1:** Study Treatment Groups

Treatment Group	Treatments	Dose Level	Planned No. of Subjects
1	QVLP adjuvanted with AS03	30 μg/strain	40
2	QVLP unadjuvanted	30 μg/strain	40
3	Fluzone HD Quad	60 μg/strain	40

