#### 4. General Statistical Considerations

Continuous data (absolute values and change from baseline values) will be described using descriptive statistics (i.e., n, mean, standard deviation (SD), median, minimum, and maximum). Categorical data will be described using frequency count and percentage in each category. For the summary statistics of all numerical variables unless otherwise specified, minimum and maximum will be displayed to the same level of precision as reported. Mean and median will be displayed to one level of precision greater than the data collected. Standard deviation/ standard error will be displayed to two levels of precision greater than the data collected.

For the summary statistics of categorical variables, all percentages will be rounded to one decimal place. Number and percentage values will be presented as xx (xx.x). If the percentage is 100, no decimal is required. If it is below 0.1, it will be reported as "<0.1". P-values will be rounded to three decimal places. If a p-value is less than 0.001 it will be reported as "<0.001." If a p-value is greater than 0.999 it will be reported as ">0.999."

All summary tables will have the population sample size in the column headers in form of N=XXX for each treatment group and all subjects, and the analyses of the immunogenicity and safety endpoints will include comparisons by prior influenza vaccination status, if >25% of the enrolled subjects have received a standard influenza vaccine during the 12 months prior to study vaccination. The five stopped treatment groups (QVLP adjuvanted with AS03 (half dose) 15  $\mu$ g/strain, QVLP adjuvanted with AS03 (half dose) 45  $\mu$ g/strain, QVLP adjuvanted with AS03 (half dose) 30  $\mu$ g/strain and QVLP adjuvanted with AS03 45  $\mu$ g/strain) will also be included in analyses as other treatment groups. All enrolled subject data recorded on CRF and entered into the database will be provided in separate data listings showing individual subject values. Data will be displayed in all listings sorted by treatment group, subject number and visit (time point, if applicable).

All laboratory data will be reported using international system of units (SI).

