# 4.1. Sample Size

No statistical sample size calculations were performed. The determined sample size up to approximately 120 subjects with 40 subjects in each treatment group will make it possible to perform the initial evaluation of vaccine immunogenicity and detect sizable differences in rates of adverse events since objective of this study is to quantify the type, percentage, intensity, duration, and relationship of common post-vaccination safety events to determine if they differ clinically among the treatment groups.

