#### 9.3. Unsolicited Adverse Events

An adverse event (AE) is defined as any untoward medical occurrence in a subject or clinical investigation subject who was administered a pharmaceutical product, with or without a causal relationship with the treatment.

For the purpose of inclusion in AE tables, incomplete data will be imputed based on section 4.3. Subsequently, AEs might be reclassified as medical history based on the rules described in the same section.

All AEs will be classified by System Organ Class (SOC) and Preferred Term (PT) according to the Medical Dictionary for Regulatory Activities (MedDRA, version 23.1 or later).

Summaries of the number and percentage of subjects with AEs will be provided by SOC (in internationally agreed order) and PT (in alphabetical order) separately. At each level of subject summarization, a subject is counted once if the subject reported 1 or more events.

Percentages will be calculated out of the number of subjects in the SAS population.

Subjects with at least 1 AE will be summarized by treatment group as a whole.

For the following categories, AE information will specifically be presented by gender (Both, Male and Female), race (All, Caucasian or White; Black or African American; Asian) and prior vaccine status (Both, Yes and No), if >25% of the enrolled subjects have received a standard influenza vaccine during the 12 months prior to study vaccination, for the overall population (65 years of age and older):

- Unsolicited AEs for 28 days following study vaccine administration;
- Immediate unsolicited AEs up to 30 minutes after vaccination;
- SAEs;
- Related Hypersensitivity Reactions (AESI);
- Narcolepsy
- pIMDs and Other AESI;
- MAAEs;
- NOCD;
- AEs leading to study discontinuation;
- AEs leading to death;
- Most frequent (defined as  $\geq 1.0$  % of subjects in one of AdjQVLP treatment groups) unsolicited AEs within 28 days after vaccination.

Subject AE data including specific details will be presented in listings.

Medicago USA Page 37 of 55

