# 13.2. Overview of Randomization Strategy

The description below reflects the randomization strategy before protocol version 3.0.

Note: the five stopped treatment groups (QVLP adjuvanted with AS03 (half dose) 15  $\mu$ g/strain, QVLP adjuvanted with AS03 (half dose) 45  $\mu$ g/strain, QVLP adjuvanted with AS03 15  $\mu$ g/strain, QVLP adjuvanted with AS03 (half dose) 30  $\mu$ g/strain and QVLP adjuvanted with AS03 45  $\mu$ g/strain) were also considered at time of the two IDMC meetings for decision making.

Below list details steps of decision making in chronological order which are to be followed throughout the duration of the study:

- 1. Schedule 1 open: 18 records (3 subjects per treatment groups 1-6)
- 2. Schedule 1 closed
- 3. 1st IDMC
  - If IDMC1 doesn't permit group 7-8 then open schedule 1 (47 subjects per treatment groups 1-6) and study complete
  - If IDMC1 permits group 7-8 then continue as below:
- 4. Schedule 2 open: 6 records (3 subjects per treatment groups 7-8)
- 5. Schedule 2 closed
- 6. Schedule 1 open 282 records (47 subjects per treatment groups 1-6)
- 7. 2nd IDMC
  - If IDMC2 doesn't permit group 7-8 then continuing open schedule 1 (47 subjects per treatment groups 1-6) and study complete
  - If IDMC2 permits group 7-8 then
    - o If group 1-6 is fully enrolled, close Schedule 1 and open Schedule 2 (94 subjects per treatment groups 7-8)> study complete
    - If group 1-6 is not fully enrolled, continuing open schedule 1 till fully enrollment is reached, close Schedule 1 and open Schedule 2 (94 subjects per treatment groups 7-8)> study complete

Numbering of treatment groups in above description is as follows:

QVLP adjuvanted with AS03 15 μg/strain**	1
QVLP adjuvanted with AS03 (half dose) 15 μg/strain*	2
QVLP adjuvanted with AS03 30 μg/strain	3
QVLP adjuvanted with AS03 (half dose) 30 μg/strain**	4
QVLP unadjuvanted 30 μg/strain	5
Fluzone HD Quad 60 µg/strain	6

Medicago USA Page **46** of **55** 

QVLP adjuvanted with AS03 45 μg/strain**	7
QVLP adjuvanted with AS03 (half dose) 45 μg/strain*	8

\*Enrollment into these 2 treatment groups was stopped as per protocol version 3.0.

Medicago USA Page 47 of 55

\*\*Enrollment into these 3 treatment groups was stopped as per protocol version 4.0.

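### The SAP's table of most frequent unsolicited AEs applies a 1.0% cut-off to the adjuvanted groups only: it filters out no adjuvanted term and removes only comparator-only terms

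*SAP*

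**What the plan says.** SAP 9.3 lists the AE categories to be broken down by gender, race and, if the vaccination-history condition is met, prior vaccine status. The last is the most frequent unsolicited AEs, which the SAP defines as those in at least 1.0% "of subjects in one of AdjQVLP treatment groups) unsolicited AEs within 28 days after vaccination". No comparator group appears in that definition.

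Protocol 12.5.1 has the same item, "Most frequent unsolicited AEs within 28 days after vaccination", with no threshold and no restriction to particular groups.

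On group size, SAP 4.1 plans "approximately 120 subjects with 40 subjects in each treatment group", and SAP 3.1 records that "the planned number of subjects has been decreased 50 to 40 by treatment group". SAP section 4 says of the five stopped groups, all adjuvanted, that they "will also be included in analyses as other treatment groups". Six adjuvanted groups can therefore qualify a term.

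The list in SAP 9.3 also opens with all unsolicited AEs over 28 days, with the same splits and no frequency filter. SAP 9.3.2 tabulates unsolicited AEs to Day 28 by intensity, system organ class and preferred term. All AE data are listed.

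**The concern.** A frequency cut-off should set common terms apart from isolated reports, and a table laid out by treatment group should choose its rows by a rule that treats the groups alike. This rule appears to do neither. If one subject always exceeds 1.0%, nothing seen in an adjuvanted group is screened out. If only adjuvanted groups count, a term common in a comparator but absent from every adjuvanted group has no row.

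The primary safety objective compares the adjuvanted vaccine with both comparators. SAP section 9 makes the safety analysis purely descriptive, so the choice of rows shapes what a reader sees. A reader who took this table as a fair picture of common events would see terms found only in adjuvanted recipients but never terms found only in comparator recipients.

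**Working it through.** **Inputs**
- Cut-off: at least 1.0% in one adjuvanted group (SAP 9.3).
- Group size n: 40 planned (SAP 4.1), earlier 50 (SAP 3.1).
- Largest conceivable group: SAP 13.2 has "94 subjects per treatment groups 7-8". SAP 3.1 treats the 94 as both groups together, so 47 + 3 = 50 each. Read instead as 94 per group, the size is 94 + 3 = 97.
- Denominator: the safety analysis set (SAP 9.3).

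The 1.0% has no derivation in the documents, so there is no calculation of the plan's to reproduce. The planned total agrees with the group sizes: 3 × 40 = 120.

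**Step 1: can the cut-off exclude anything?** One subject is 100/n per cent, and the smallest count that qualifies is 1.0 × n/100 rounded up.

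| n | one subject | smallest qualifying count |
|---|---|---|
| 40 | 2.5% | 1 |
| 50 | 2.0% | 1 |
| 97 | 1.03% | 1 |
| 100 | 1.0% | 1 |
| 101 | 0.99% | 2 |

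A single report falls below the cut-off only from n = 101. The sizes reached by the stopped arms are not given, but a smaller arm only raises 100/n.

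**Step 2: what does the rule remove?** By step 1, a term qualifies exactly when at least one adjuvanted recipient reported it. The terms in the full 28-day table but not in this one are therefore those with no adjuvanted report and at least one comparator report. Removing them is the rule's only effect. With 0 in every adjuvanted group, a term is absent at 4/40 = 10% in Fluzone HD Quad, and also at 6/40 = 15%. The two-sided Fisher p for 0/40 against 6/40 is 0.026, given only for scale because the SAP tests no safety data.

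**Step 3: how often would a term be comparator-only by chance?** Assume the same true rate p in every group, 40 adjuvanted and 80 comparator subjects, and no stopped arms. The chance is (1 − p)^40 × [1 − (1 − p)^80].

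| assumed p | no adjuvanted report | at least one comparator report | comparator-only |
|---|---|---|---|
| 1% | 0.669 | 0.552 | 37.0% |
| 2.5% | 0.363 | 0.868 | 31.5% |
| 5% | 0.129 | 0.983 | 12.6% |
| 10% | 0.0148 | 0.9998 | 1.5% |

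These chances fall once the stopped arms are counted, because any one of them can also qualify a term.

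**Step 4: would a 5% rule filter?** 5% of 40 is 2 subjects. 5% of 50 is 2.5, so 3 subjects. Single reports are excluded. In an arm of 20 or fewer, one subject is 5% or more, so a minimum count is also needed.

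**The case against.** The strongest reply is that the SAP already shows what this table omits. The unfiltered 28-day category stands in the same list with the same splits, and the intensity tables and listings apply no frequency filter. The 4/40 example would appear in all of them. That stands, and it limits the point to one table.

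Four stronger readings might tempt a reader. The documents support none of them.
- **The primary safety endpoint is distorted.** It is not: that endpoint covers all unsolicited AEs for 28 days (Protocol 10.2.2.1, SAP 3.2.1), and no test or decision rule rests on the most frequent table.
- **An adjuvanted-vaccine signal could be hidden.** It could not: every adjuvanted term passes, and the asymmetry runs against the investigational vaccine.
- **The SAP contradicts the protocol.** The protocol leaves the term undefined and defers complete details to the SAP (Protocol section 12). This is a poor specification, not a conflict.
- **The 1.0% was carried over from Protocol 1.3.1.** That section uses the same figure for "unsolicited TEAEs within 21 days of vaccine administration included arthralgia" in studies with 14 409 QVLP recipients, where it can filter. The documents do not say that it was the source.

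It is also fair to say that omission by chance is likely mainly for uncommon terms, which a table of common events need not show. But the rule keeps equally uncommon terms when an adjuvanted recipient reports them, so the imbalance remains.

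**Conclusion.** The definition in SAP 9.3 does not do what its label says. At 40 to 50 per group the 1.0% cut-off excludes no adjuvanted term, and it could do so only above 100 per group. Because the comparators cannot qualify a term, the table equals the full 28-day table minus comparator-only terms. It does not isolate common events and cannot be read comparatively.

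The consequence is small: one descriptive table is affected, no event is lost from the report and no adjuvanted event is concealed. It is still worth correcting, because the rule as written gives a mislabelled, one-sided table and the remedy needs no data.

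The filtering result depends only on groups having 100 subjects or fewer. The one-sidedness rests on reading AdjQVLP as adjuvanted QVLP, which is the natural sense although the SAP's abbreviation list does not define it. The chances in step 3 rest on assumed equal rates and leave out the stopped arms.

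**What to change.** Replace the definition in SAP 9.3 with a symmetric one. For example, select preferred terms reported by at least 5% of subjects, and by at least 2 subjects, in any of the three retained groups (adjuvanted 30 µg/strain, unadjuvanted QVLP, Fluzone HD Quad). For each selected term show every treatment group, including the stopped arms, in keeping with SAP section 4. The 5% is a proposed value, not one taken from the documents; the sponsor may prefer another, provided that one subject cannot meet it and the comparators count.

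Letting only the retained groups qualify terms keeps a small stopped arm from bringing single reports back in. The price is that a term confined to a stopped arm would not be selected, though it stays in the unfiltered table.

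The cost is one sentence, a table footnote and a programming change, with no new data. SAP section 10 includes all tables in the Day 28 interim analysis, and SAP 4.2.2 lets some sponsor Biostatistics and Safety staff see unblinded data during the study. The change should therefore be dated and recorded in SAP section 11 as made after those tables were planned, and before the final database lock.
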